6.3 Study flow diagram

6.4 Schedule of assessments

Description	Investigation	Baseline assessment	Follow up assessment	Telephone assessment
Clinical review	Patient demographics	X		
	Disease characteristics	X		
	Patient co-morbidities	X		
	Assessment of PS	X	X	
	Medication history	X	X	X
	Oncological treatment history	X	X	X
	Pleural intervention history	X	X	X
PROMS	Breathlessness VAS	X	X	X
	Chest pain VAS	X	X	X
	Sweats VAS	X	X	X
	EQ-5D-5L QoL score	X	X	X
Blood tests	FBC	X	X	
	U&E	X	X	
	LFT	X	X	
	CRP	X	X	
	LDH	X	X	
	Total protein	X	X	
	Random glucose	X	X	
	CMV IgM/IgG	X*		
	White blood cell phenotyping	X*		
	CMV viral load	X*		
Imaging	TUS	X	X ⁺	
	CXR	X	X ⁺	X ⁺
	CT Thorax (minimum every 6 months)	X	X ⁺	X ⁺
Pleural fluid assessment (if present)	Total protein	X*	X*	
	LDH	X*	X*	
	Glucose	X*	X*	
	Cytology	X*	X*	
	Review of drainage diaries	X*	X*	X*
Pleural biopsies (if available)	Retrieval of FFPE sample from pathology services	X		
	Core samples stored for TMA	X		
	Unprocessed sample(s) stored in RNA Later	X		
Pleural biopsies tests (if available)	Immunohistochemical and FISH testing of protein and genetic markers	X*		
	Histological assessment of grade, necrosis and other prognostic factors	X*		
Storage of samples	Blood sample for storage	X	X	
	Pleural fluid for storage	X	X	
Trial review	Assessment of eligibility for any current trials, including screening blood tests	X	X	X*
	Documentation of trial participation	X	X	X*
Consent	Verbal consent for ongoing participation		X	X
X = required X* = if applicable X⁺ = at clinician's discretion, ideally every 4 months				

6.5 Telephone/postal assessments

Participants who are unable to attend regular study follow up appointments, either as a result of frailty or geographical distance from a study centre (including participants identified from PICs), may undergo telephone or postal follow up. Telephone appointments will be undertaken by a research nurse, or any member of the research team. Assessments will include a brief clinical review covering any oncological treatments received or pleural procedures undergone since the previous assessment, and review of pleural fluid drainage diaries for participants who have an IPC in situ. Symptoms will be reviewed, and EQ-5D-5L QoL questionnaire and VAS scores will be completed verbally. Alternatively VAS scores and QoL questionnaires may be sent through the post for completion by the participant in their own time. Assessment of eligibility for trials will be undertaken, if appropriate.

Participants who are undergoing telephone assessments and wish to be considered for clinical trials must be willing and able to attend trial visits at the appropriate trial centre.

6.6 Questionnaires & patient reported outcomes

Participants will complete the EQ-5D QoL questionnaire at every trial visit. The EQ-5D-5L is a widely used preference-based generic health-related QoL instrument and is the instrument favoured by the National Institute of Health and Care Excellence (NICE).³⁵ It measures QoL on 5 dimensions (mobility, self-care, usual activities, pain/discomfort and anxiety/depression) with 3 severity levels for each dimension, producing a possible 243 health states. A utility score can be generated for each health state by applying country-specific general population-elicited tariffs, which can then be used to calculate quality-adjusted life years. This data set used the UK population EQ-5D-5L tariff.³⁶ EQ-5D-5L has been applied to mesothelioma in clinical trials of surgical interventions, radiotherapy and palliative care, as well as being used in previous mesothelioma cohort studies.³⁷⁻⁴⁰

Patient reported symptoms of breathlessness and chest pain will be recorded at each study visit. Symptoms will be reported on a 10cm VAS with anchored at zero - “no pain/breathlessness” and 10 “worst pain/breathlessness imaginable”. VAS are a validated tool for assessing breathlessness and chest pain in malignant pleural disease and are acceptable to patients.^{41 42} Despite being a well-recognised symptom of mesothelioma, the frequency and severity of sweating has not been evaluated in patients with mesothelioma before. Its inclusion in the cohort assessment is a result of patient feedback during a public engagement event. It is hoped that collecting this data will provide information into the prevalence of this symptom and its relationship to survival and other clinical outcomes. The VAS for sweating will be similar to the VAS for pain and breathlessness and will be based on existing VAS used to assess hyperhidrosis and associated conditions.

6.7 Biological samples

Participants will be asked to give their consent for blood and pleural fluid samples to be collected and stored for use in the current study and future research, both in the UK and overseas. Consent will also be requested for access to surplus biopsy tissue, not required for diagnostic or therapeutic purposes. A hierarchy of access will be followed to ensure that local clinical diagnostic services have first access to tissue, with ASSESS-meso receiving additional tissue only if it is available.

Certain tests (e.g. blood haematology and biochemistry, pleural fluid biochemistry, and flow cytometry) will be run on the day the sample is obtained. Blood analysis for circulating tumour cells will be analysed according to study specific procedure 12 – sample processing for UBC sub-study. Further blood and pleural fluid samples will be stored for future analyses, including but not limited to cytokine levels, immune cell population assessment and phenotyping, tumour metabolites and receptor status, and epigenetic biomarkers to assess for any associations with progression of disease and mortality.

Additional DNA extraction and genetic analysis will be performed on blood, pleural fluid and tissue samples where the study participants have provided their consent to allow this.

Biological samples will be collected by research nurses, clinicians and members of the study team as required for routine clinical care. Research samples will be processed and stored as described in the relevant study specific procedures. All samples will be stored anonymised, identifiable by ASSESS-meso study number and a study specific bar-code only. The code sheet will be stored securely, in a separate location to the samples.

Study specific procedure documents will be provided to all sites involved in the processing and storage of biological samples,

Study samples may be sent to laboratories outside of the trial centres (including overseas) for processing and for tests to be performed. All samples sent for analysis, and any data sent with the samples, will be anonymised and labelled with the ASSESS-meso study number. Samples will be transported by first class post in accordance with UN 3373 regulations, under the classification Biological substance, Category B. All samples will be transported in compliance with 49 CFR, Part 173.199 and/or IATA Packing Instruction 650 approved regulations.

Samples will be stored, with participants' consent, at local sites prior to batch transport to North Bristol NHS Trust. Participants will be asked to consent to storage of their samples and for their samples to be used in other research studies and/or shared with other researchers (including overseas), once ASSESS-meso has finished.

6.7.1 Biopsy samples

A sample of diagnostic biopsies will be retrieved as described in 6.1. These will be assessed histologically for nuclear grade, necrosis and other prognostic factor, and undergo immunohistochemical and FISH testing of protein and genetic markers.

6.8 Cessation of follow up

Follow up assessments will cease if the participant withdraws from the study, or if the participant dies. The research team will receive regular cancer/death notifications from the NHSCR and the NHSIC. The registers will notify us of subsequent cancer registrations and mortality among cohort members throughout the study. Where sites have become aware that a patient has died, they will notify the ASSESS-meso team. A mortality form will be completed for each deceased patient.

It is possible that participants will become increasingly frail as they approach the end of their life, and the demands of ongoing cohort follow up may be too onerous for them. These participants should be offered the longest interval between study assessments (i.e. 4 months). If this schedule still proves too burdensome, then they will be invited to participate in telephone follow up. If they do not wish to do this, they will be invited to withdraw from the study. They will be asked whether they are happy for their existing data and biological samples to be kept as part of the

study. They will also be asked whether they consent to a member of the research team accessing their medical records via online registries to determine date of death. Further information on withdrawal from the study is described in Section 9.

6.9 Study duration

The cohort study will run for 10 years or until a total of 700 participants have been recruited, whichever happens first. Participants who consent to join the cohort will remain under follow up until death, or withdrawal from the study. Since median life expectancy with MPM is approximately 1 year from diagnosis, it is anticipated that the cohort population will be dynamic, and the cohort will be a continuously “rolling” as new participants are enrolled, and other participants leave the cohort, either as a result of withdrawal or mortality.

6.10 Source data

The primary data source will be the participant’s medical notes. The laboratory reports will form the primary data source for blood results. The CT scan report will form the primary data source for any scans. Patient-reported outcome measures, such as symptoms, quality of life and pleural fluid drainage, will use the individual participants’ diaries as source data.

Electronic case report forms (CRFs) will be used to collect data at each study visit. Paper checklists will be provided to each study centre to use as a prompt for electronic CRFs if desired. Completed checklists are not classified trial documents and can be filed in the patients’ notes to act as source data or stored or destroyed at the respective study centre. At the end of the study, all essential documents will be archived locally by participating sites, in accordance with NBT’s archiving SOP (RI/QMS/SOP/010, available at <https://www.nbt.nhs.uk/sites/default/files/sites/default/files/RI%20QMS%20SOP%20010%20-%20Archiving.pdf>).

7. STATISTICAL ANALYSIS PLAN

We will use multiple linear regression to compare continuous outcomes; logistic regression to compare dichotomous outcomes and Cox’s proportional hazards to compare survival between different groups controlling for confounding factors. We will use random effects models or robust estimates to allow for clustering between centres. Outcomes with repeat measurements will be analysed using regression modelling with adjustment for baseline values.

The sensitivity, specificity, NPV and PPV for predicting disease progression will be assessed at established cut-off levels for serum and pleural fluid biomarkers, cytokines, immune profile, receptor status and epigenetic markers. Receiver operator characteristic curves will be drawn. The gold standard for disease progression will be confirmation of progressive disease made at the regional mesothelioma MDT meeting.

An interim analysis will be undertaken once recruitment reaches 25% of target (i.e. n=175), describing the baseline characteristics of participants, and evaluating generalisability of the cohort population with comparison to existing real-world cohorts, e.g. National Lung Cancer Audit Mesothelioma Report.

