5. METHODOLOGY

5.1 Setting

The cohort will be established at 2 centres initially; North Bristol NHS Trust Pleural Service (NBT) and Oxford Respiratory Trials Unit (ORTU). Both of these centres have established track records in recruiting patients to mesothelioma trials and have appropriate research infra-structure in place to recruit to the cohort. The lead clinicians ([name] at NBT and [name] at ORTU) are experienced senior investigators with extensive clinical experience in pleural disease and MPM. Both centres hold dedicated pleural clinics, which receive regional referrals for MPM. Both centres also host regional mesothelioma multidisciplinary team (MDT) meetings in which new cases of MPM are discussed.

In addition to the two trial centres, there will be a number of participant identification centres (PIC) who refer patients for discussion at the regional mesothelioma MDT. These will include (but not be limited to) University Hospitals Bristol NHS Trust, Gloucester Hospitals NHS Foundation Trust, Weston Area Health NHS Trust, Taunton and Somerset NHS Foundation Trust, Yeovil District Hospital NHS Foundation Trust and Royal United Hospitals Bath NHS Foundation Trust.

Once approximately 100 participants have been recruited from these two centres, other centres will be invited to become recruiting centres for the study. It is anticipated that these additional centres will cover a wide geographical area across England.

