6.2 Follow up assessments

Study assessments will be undertaken when the participant attends for review as part of standard clinical care. This should happen every 3 months as a minimum. Some participants will require more frequent follow-up for clinical reasons and will therefore undergo more frequent assessment. Participants who are eligible for participation in future TwiCs may be invited to attend more regular study assessments at one of the study centres, in accordance with the follow up schedule for that specific TwiC.

[figure not shown]
At each visit participants will undergo clinical assessment, including review of symptoms, medication history, oncological treatment received, details of any pain interventions, any engagement with Specialist Palliative Care teams and change in clinical status. Blood tests will be taken for FBC, U&E, LFT, CRP and random glucose,. A sample of blood will be taken for storage. Pleural fluid drainage diaries will be reviewed and documented. Participants who have an indwelling pleural catheter in situ or who are undergoing pleural aspiration for clinical reasons will have pleural fluid biochemistry tested and have a sample of pleural fluid taken for storage. Participants will complete PROMS for QoL and VAS scores for chest pain, breathlessness and sweats. Intermittently participants will be invited to complete daily VAS scores from home and will be provided with a VAS booklet to complete.

Radiological imaging, including CXR, CT thorax and bedside TUS will be undertaken at the discretion of the clinician, based on clinical need. It is anticipated that participants will have a CXR, TUS or both at every clinic appointment as part of routine care. It is expected that participants will have a CT scan every 6 months as a minimum for routine clinical care. If a participant has more frequent CT scans, for clinical reasons, these images will be collected as part of the study.

At each follow up assessment, cohort participants will be assessed for their eligibility to participate in any trials (TwiCs) that are currently underway within the cohort. Any participant who meets the eligibility criteria for a TwiC will be provided with a PIS for that trial and given the opportunity to discuss it with a member of the trial team. As part of the screening process, additional blood samples or investigations may be undertaken to determine or confirm eligibility for specific trials. These activities are deemed ASSESS-meso

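### Plain centre-robust standard errors are unreliable with few or very unequal centres, and the plan names no patient-level term for repeated outcomes

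*Protocol*

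**What the plan says.** Protocol section 7 names linear, logistic and Cox regression, and then deals with correlation in two sentences. On centres: "We will use random effects models or robust estimates to allow for clustering between centres". On longitudinal outcomes: "Outcomes with repeat measurements will be analysed using regression modelling with adjustment for baseline values". Centre is the only level of clustering mentioned.

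On the number of centres, section 5.1 says "The cohort will be established at 2 centres initially", and that after roughly 100 participants "other centres will be invited to become recruiting centres for the study". It adds: "It is anticipated that these additional centres will cover a wide geographical area across England". No final number is given. Section 5.6 expects about 50 recruits a year from the two lead centres, a target of 700, and completion within 10 years once others join.

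On repeat measurements, sections 6.2, 6.4 and 6.6 have EQ-5D and symptom VAS recorded at each assessment. On the interval between assessments, section 6.2 says "This should happen every 3 months as a minimum".

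**The concern.** Two separate matters are involved.

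First, a cluster-robust variance is estimated from one score contribution per centre. With few centres, or with a couple of large ones holding most of the patients, that estimate is biased downwards and unstable, so tests reject too often. Section 7 offers this method on equal terms with random effects and sets no condition, in a study whose centre structure is open and probably lopsided.

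Second, for VAS and EQ-5D the strongest correlation is between visits of the same patient. Adjusting for the baseline value reduces that correlation but does not remove it, and a centre term does not address it. Longitudinal data are the first stated aim of the cohort, so intervals for patient or treatment factors on these outcomes matter.

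**Working it through.** **The plan's own figure.** For 38% v 50% one-year survival, two-sided 0.05 and 80% power, the unpooled formula gives 7.849 × (0.38×0.62 + 0.50×0.50) / 0.12² = 265 per group; the pooled form gives 268. The stated 266 is reproduced and is not in dispute. I use its total of 532 as the analysed sample.

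**How unequal the centres could be.** Section 5.6: 50 a year × 10 years = 500 from the two lead centres; 500/700 = 71%. This is an upper scenario, because faster expansion would shorten recruitment and lower the share. Scaled to 532, it is 190 patients in each lead centre (an equal split is my assumption) and 152 shared by the rest.

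**Centre-robust tests.** Simulation with 4,000 replicates per cell: continuous outcome, null patient-level covariate split at the median, assumed centre intraclass correlation 0.02, and a sandwich variance clustered on centre with the usual G/(G−1) factor. Rejection rates at nominal 5%:

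| Centres (G) | Equal sizes, normal critical value | Lead centres hold 71%, normal critical value | Same, t with G−1 df | Centre as fixed effect |
|---|---|---|---|---|
| 2 | 29% | – | – | 5% |
| 4 | 14% | 16% | 6% | 5% |
| 6 | 11% | 15% | 8% | 5–6% |
| 10 | 9% | 15% | 11% | 5% |
| 20 | 6% | 14% | 12% | 5% |

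Repeat runs differ by about a point, hence 11–15% for 4–6 equal centres. With equal centres the t reference restores about 5% at every G. Under the imbalance (4, 6 and 20 centres), intraclass correlations of 0.01 and 0.05 give 13–16% with the normal critical value, so the result hardly depends on that assumption.

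**Centre random intercept (REML).** With one measurement per patient, 95% intervals for a patient-level covariate covered 95% with 2 centres, 94% with 4 and 96% with 10. Fits often gave boundary or convergence warnings, but the intervals were not too narrow.

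**Repeated outcomes.** Assume 4 follow-up visits: three-monthly visits over about one year, in line with section 6.9 ("Since median life expectancy with MPM is approximately 1 year from diagnosis"). Let ρ be an exchangeable within-patient correlation. Given baseline, the residual variance is 1−ρ² and the covariance ρ−ρ², so the residual correlation is ρ(1−ρ)/(1−ρ²) = ρ/(1+ρ). The design effect is 1 + 3ρ/(1+ρ), and the coverage of a nominal 95% interval is 2Φ(1.96/√DE) − 1.

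| ρ (assumed) | Residual correlation | Design effect | SE as share of correct SE | Coverage |
|---|---|---|---|---|
| 0.3 | 0.23 | 1.69 | 77% | 87% |
| 0.5 | 0.33 | 2.00 | 71% | 83% |
| 0.7 | 0.41 | 2.24 | 67% | 81% |

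Fewer visits soften this: 3 visits at ρ = 0.5 give a design effect of 1 + 2×0.33 = 1.67 and coverage of about 87%. In simulation at ρ = 0.5 with 4 visits, a centre-only random intercept left coverage at 83.5%, while clustering by patient restored about 95%. Centre-robust errors do absorb nested patient correlation with 20 equal centres (95% coverage), but with 20 centres at the imbalance above the type I error was still 14.5%.

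**The case against.** Several stronger readings are tempting, and the protocol does not support them.

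- *The study has only two centres.* Two is the starting state. Section 5.1 plans expansion, and the one interim analysis (n = 175) is descriptive, so the 29% figure belongs to no planned test.
- *Random effects fail in the same way.* They do not. The centre variance is poorly estimated, but coverage for patient-level covariates stays near 95%. Section 7 names this option first, so an analyst may choose it and avoid the problem.
- *Intervals will be too narrow.* The wording on repeat measurements does not exclude a mixed model, GEE or a comparison at a single time point, and nothing says that visits will be pooled as independent rows. A separate statistical analysis plan may settle it. Single-measurement linear, logistic and Cox analyses, including the survival comparison behind the sample size, do not have the repeated-measures problem.
- *Sicker patients will dominate pooled data.* Section 6.2 does say "Some participants will require more frequent follow-up for clinical reasons and will therefore undergo more frequent assessment". But section 6.8 gives frail participants the longest interval and then telephone follow-up, and early death shortens a series. The net direction is unknown.

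A small-sample reference distribution also repairs the robust test when centres are equal in size. It does not do so under the imbalance that the recruitment figures allow (12% at 20 centres).

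All of this stands. What it leaves is that section 7 expressly permits plain robust errors over centres without condition, and that its only named devices for repeated outcomes do not cover within-patient correlation.

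**Conclusion.** The concern holds in limited form. Plain centre-robust inference is a poor option for this study: about 11–15% type I error with 4–6 equal centres, and about 14–16% with 4–20 centres if the two lead centres supply some 71% of patients, against about 5% with centre as a fixed effect. For repeated outcomes the point is conditional: if visits were pooled with only baseline adjustment and centre clustering, 95% intervals would cover about 81–87%.

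The centre intraclass correlation, the final number and sizes of centres, the visit count and the within-patient correlation are all assumptions; the protocol gives none of them. The simulations use a continuous outcome. The same weakness of a sandwich variance applies in principle to Cox and logistic models, but its size there was not computed. The sample size is unaffected.

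**What to change.** Amend two sentences in section 7.

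1. Centre: fit it as a fixed effect in linear and logistic models and as a stratum in Cox models, or as a random effect. Drop plain centre-robust errors unless many centres of reasonably balanced size have joined.
2. Repeated outcomes: state a mixed model with a patient random effect, or GEE or standard errors clustered by patient, with the baseline value as a covariate.

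Joint modelling with death, random slopes, or a fixed minimum number of centres for using random effects are matters of preference and are not needed to resolve this point.

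The change is to wording only. The price is a few degrees of freedom for centre; no data collection or recruitment target changes.
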